20.9 Time Points for Data Analysis

20.9.1 Length of Follow-up for PMA Study Data Analysis

Safety and effectiveness will be evaluated at the Interim Analysis and at 1 year.

20.9.2 Length of Follow-up for Durability Data Analysis

Long-term data will be collected annually through 5 years.

20.10 Statistical Analysis Plan

The details for the Statistical Analysis Plan are provided in **Appendix 19**.

21.0 REGULATORY AND REPORTING REQUIREMENTS

21.1 Adverse Events and Reporting

An adverse event (AE) is an untoward medical occurrence in a patient or clinical investigation participant receiving a procedure using a medical device and that does not necessarily have a causal relationship with the treatment. An adverse event can therefore be any unfavorable and unintended sign (including an abnormal laboratory finding), symptom, or disease temporally associated with the use of a medical device, whether or not related to the medical device. Generally, a condition is an adverse event if it is undesirable and was not present before the participant underwent the procedure or is more severe than before the participant underwent the procedure, and/or is more frequent than before the participant underwent the procedure.

Adverse event information will be collected over the entire duration of the study. Collection of adverse event data will commence upon random assignment of a study participant. The following information will be recorded on the appropriate case report form:

- Event diagnosis or syndrome
- Date of onset
- Duration
- Severity (mild, moderate, or severe)
- Relationship to the device (not related, possibly related, probably related, related, or unknown)
- Relationship to the procedure (not related, possibly related, probably related, related, or unknown)
- Action taken, and
- Outcome (not resolved, resolved with sequelae, or resolved).

If the diagnosis or syndrome is not known, the unfavorable or unintended sign or symptom experienced by the participant should be recorded on the CRF. Adverse events will be determined by the study investigator treating the study subject. Adverse events will be monitored and treated as appropriate until the event has subsided or, in case of permanent impairment, until the event stabilizes and the overall clinical outcome has been ascertained. Adverse events will be followed until resolution or until the end of the study. In addition, all IRB and FDA reporting requirements will be followed.

21.2 Serious Adverse Events and Reporting

A serious adverse event (SAE) is any untoward medical occurrence that:

- Results in death,
- Is life-threatening,
- Requires inpatient hospitalization or prolongation of existing hospitalization, or
- Results in persistent or significant disability/incapacity, or congenital

anomaly/birth defect.

All serious adverse events should be reported immediately (within 24 hours of knowledge of the event) to the study sponsor. All IRB and FDA reporting requirements will be followed.

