11.6 Post-Bronchoscopy Recovery Period Procedures for Study Treatment Arm

Study participants who receive the study treatment will be required to stay in the hospital for at least 5 nights. During the hospital stay, chest X-rays will be obtained daily, including a chest X-ray at Day 0, Day 1, Day 2, Day 3, Day 4, and Day 5. If a study participant is being treated for a pneumothorax during the study procedure hospital stay, collection of chest X-rays beyond Day 5 will be at the discretion of the study physician, with a protocol mandated chest X-ray on the day of discharge. An overview of the post-procedure hospital stay for study participants who receive the study treatment is shown below.

Post-Study Procedure Checklist For Coordinators

Day 0-Post-Study Procedure

_____ Ensure that patient is transferred to appropriate recovery area as per local hospital's standard protocol.

- _____ Ensure that chest x-ray is obtained and reviewed by treating physician within 1 hour (\pm 30 minutes) of procedure for assessment of volume reduction and pneumothorax.
- _____ Ensure that patient receives antibiotics, corticosteroids, bronchodilators, or any other medications as needed.
- _____ Ensure that vital signs and pulse oximetry are recorded and assessed during the 24 hours following the procedure.
- _____ Ensure that patient is assessed for any adverse events.

Day 1-Hospital Stay

- _____ Ensure that chest x-ray is obtained and reviewed by treating physician for assessment of volume reduction and pneumothorax.
- _____ Ensure that ABG and serum fibrinogen samples have been collected.
- _____ Ensure that patient completes Daily Diary.
- _____ Ensure that patient is assessed for any adverse events.

Day 2-Hospital Stay

- _____ Ensure that chest x-ray is obtained and reviewed by treating physician for assessment of volume reduction and pneumothorax.
- _____ Ensure that patient completes Daily Diary.
- _____ Ensure that patient is assessed for any adverse events.

Day 3-Hospital Stay

- _____ Ensure that chest x-ray is obtained and reviewed by treating physician for assessment of volume reduction and pneumothorax.
- _____ Ensure that patient completes Daily Diary.
- _____ Ensure that patient is assessed for any adverse events.

Day 4-Hospital Stay

- _____ Ensure that chest x-ray is obtained and reviewed by treating physician for assessment of volume reduction and pneumothorax.
- _____ Ensure that patient completes Daily Diary.

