15.2 Serious Adverse Events

An adverse event is considered serious if it meets the definition of a serious adverse event (SAE) as defined in Section 21.2. Serious adverse events may occur at any time during the study and will be reported as serious regardless of when they occur, provided they meet the definition of a serious adverse event.

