15.3 Management of Selected Anticipated Adverse Events

15.3.1 Pneumothorax

Pneumothorax is an expected and anticipated event in patients undergoing a lung volume reduction procedure. With lung volume reduction surgery (LVRS), pneumothorax occurs in all (100%) cases and all patients leave the operating room with a chest tube(s) to manage air leaks. After EBV treatment, it is anticipated that the collapsed lung in the target lobe or expanding lung in adjacent lobe(s) may develop an air leak(s). With lung volume reduction procedures, achieving a higher success rate may be associated with having a higher risk of pneumothorax.

In the VENT study, pneumothorax was seen in 15%-20% of EBV-treated study participants who were thought to have little or no lobar CV (i.e. had HRCT suggestive of complete fissure) along with HRCT evidence of lobar occlusion with valve treatment. Therefore, it is anticipated in this study that approximately one in five of EBV-treated study participants may experience a post-procedure pneumothorax.

Study participants who received the study treatment will be provided with a Medical Alert Card, Treated Study Participant Bracelet, Transferring Instructions if Late Pneumothorax, and Post-Procedure Instructions prior to hospital discharge. Study participants who received the study treatment will be contacted during the 10 days after discharge and asked about increased chest pain, nausea, and new, worsening shortness of breath, which are all potential indicators of pneumothorax.

A suggested treatment plan for managing any suspected pneumothorax is provided in **Appendix 18**. Any study participant who has a persistent pneumothorax requiring care beyond a chest tube should be transferred to the treating hospital and attended to by the treating physician and his or her study team.

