Adverse events will be categorized into clinically relevant groups (*e.g.:* stable pneumothorax with no intervention, pneumothorax resolved with chest tube insertion in less than 7 days,

prolonged air leak, etc.). Adverse events occurring in the treatment arm will be further categorized by severity and as device-related, procedure-related, or neither, and by those occurring during procedure hospitalization and those occurring post-discharge.

Rehospitalization rates will be reported by study arm on a Per-Patient (PPt) basis and on a Per-Event (PE) basis. In study participants who receive EBV treatment, adverse events will be evaluated by stratifying participants by use of conscious sedation and general anesthesia during the bronchoscopy procedure as well as evaluating number of valves received and sites EBV were placed.

VIII. Mortality

A Kaplan-Meier survival curve for each study arm will graphically display the time to death from the time of randomization and a log rank test will be used to compare Kaplan-Meier curves between study arms. A Cox proportional hazards model will be used to control for study site along with other significant co-variates as applicable.

IX. Patient Accountability and Missing Data

Every effort will be made to collect all data points in the study. The sponsor plans to minimize the amount of missing data by appropriate management of the prospective clinical trial, proper screening of study subjects, and training of participating investigators, monitors and study coordinators.

- The analysis for the primary endpoint will be performed by imputing missing data. Subject death prior to the 1-year visit date will be imputed as failure.
- For study participant FEV₁ data that is 'intermittent', missing outcomes will be imputed by linear interpolation using the FEV₁ value from the latest non-missing data point before the missed data point and the earliest non-missed data point after the missed data point.

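### Because only EBV recipients have a mandated hospital stay, an early complication resolved within it need not count as serious, which makes the planned SAE contrasts uneven.

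*Protocol*

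**What the plan says.** Protocol 21.2 makes an event serious if it meets any of four criteria: "Results in death"; "Is life-threatening"; "Requires inpatient hospitalization or prolongation of existing hospitalization, or"; and a fourth that begins "Results in persistent or significant disability/incapacity, or congenital". It has no criterion for an important medical event or for an intervention needed to prevent harm. Protocol 15.2 adds no rule for the index stay: events are serious whenever they occur, "provided they meet the definition of a serious adverse event".

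The arms differ in where participants are after the bronchoscopy. Protocol 11.6 states: "Study participants who receive the study treatment will be required to stay in the hospital for at least 5 nights". Its coordinator checklist places discharge at Day 5. For controls, 11.3 ends the bronchoscopy by local practice and 14.4 asks for monitoring until discharge, with no minimum stay. Crossovers follow the treatment-arm schedule once treated (7.5, 14.13).

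Early complications are foreseen. Protocol 15.3.1 anticipates that "approximately one in five of EBV-treated study participants may experience a post-procedure pneumothorax", and 11.6 provides for a pneumothorax being treated during the procedure stay.

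In the SAP, section X(b) compares SAEs in crossovers between the control year and the EBV year with a McNemar statistic, for SAEs that could occur under either. Section VII adds: "Rehospitalization rates will be reported by study arm on a Per-Patient (PPt) basis", and also per event.

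**The concern.** For most non-fatal complications in this population (pneumothorax, exacerbation, pneumonia), the hospital criterion is the usual route to being called serious. That criterion depends on where the participant is when the event starts. A control at home who needs admission meets it. An EBV recipient with the same event on Day 2 is already an inpatient, and if the event settles by the planned discharge there is neither a new admission nor, on a natural reading, a prolongation.

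The label matters where the plan uses it. SAP X(b) sets a year with no mandated stay against a year that opens with one, so the asymmetry enters only one side of a planned test. Any table of SAE rates by arm has the same feature. Rehospitalisation by arm is correctly a count of readmissions, but it understates hospital-level burden if a reader uses it for that. The 24-hour report to the sponsor in 21.2 also follows the label.

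**Working it through.** The plan gives no figure for this point, so the main check sets the rules side by side.

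**Step 1. The same event in three settings.** Take a complication that is not fatal, life-threatening or disabling, is treated in hospital, and resolves in two or three days.

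| Setting | New admission? | Stay prolonged? | Serious under 21.2? |
|---|---|---|---|
| Control at home, or crossover in the control year, admitted for it | Yes | n/a | Yes |
| EBV recipient after discharge, readmitted for it | Yes | n/a | Yes |
| EBV recipient within the mandated nights, home at Day 5 | No | No | Need not be |

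The third row depends on how the site reads the criterion. The stay in 11.6 is a minimum, and 21.2 does not say against which day prolongation is judged, so sites may classify like events differently.

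**Step 2. What this does to the McNemar comparison.** The statistic uses only discordant pairs. A crossover with no SAE in the control year and one in-stay complication that resolves before discharge is recorded as no SAE in either year and drops out. If the event had been classed as serious, the pair would be discordant against EBV.

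**Step 3. Scale, using pneumothorax only.** Inputs: 190 enrolled (SAP, Study Design), 2:1 allocation (Protocol 5.0), and about 20% expected pneumothorax, with 15% to 20% reported from the VENT study (15.3.1).

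- EBV arm: 190 × 2/3 ≈ 127. Control arm: 190 − 127 = 63.
- Expected EBV pneumothoraces: 127 × 0.20 = 25.4; at 15%, 127 × 0.15 = 19.1.
- Crossovers number at most 63, giving at most 63 × 0.20 = 12.6 in their EBV year; at 15%, 63 × 0.15 = 9.5.

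Let f be the share that is handled within the stay and meets no other criterion. The documents do not give f, so its whole range is shown. Pneumothoraces counted as serious = 127 × 0.20 × (1 − f), rounded:

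| f (assumed) | Counted as serious | % of 127 |
|---|---|---|
| 0 | 25 | 19.7 |
| 0.25 | 19 | 15.0 |
| 0.50 | 13 | 10.2 |
| 0.75 | 6 | 4.7 |
| 1 | 0 | 0 |

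The SAE count is sensitive to f, but the table does not estimate the gap between arms. Some in-stay cases, such as a stable pneumothorax seen only on a mandated daily X-ray, would not have sent a person at home to hospital, and their absence from the SAE count is not a distortion.

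**The case against.** The strongest reply is that nothing is lost. Every adverse event is recorded with onset, duration, severity, relatedness, action and outcome (Protocol 21.1). SAP VII groups events clinically, with examples that separate pneumothorax without intervention from pneumothorax resolved with a chest tube, and splits treatment-arm events into procedure stay and post-discharge. Its between-arm Fisher's tests apply to adverse events seen in at least 3% of either arm, whether serious or not. The events committee adjudicates potentially device-related events even if not serious (19.2), and the DSMB reviews all adverse events (19.1). All of this stands. A reader might infer that early EBV harm is hidden from the safety endpoint; the documents do not support that. Nor is the 3% cut-off a benchmark for missing SAEs, since it selects adverse events for testing.

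Three other strong readings also fail:

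- *That an event settled before Day 5 is definitely non-serious.* The criterion speaks of requiring inpatient hospitalisation, and an investigator or the committee could apply it to someone already admitted. The text allows exclusion but does not compel it.
- *That the bias runs one way only.* An event that delays an EBV discharge can qualify as prolongation, while the same event in a control at home might need no admission.
- *That the rehospitalisation rate is wrong.* Leaving out index-stay events is what the term means.

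It is also fair that SAP X(b) is a non-randomised, within-person contrast, and that SAP VII specifies no separate SAE test by arm. That limits the reach of the point. It does not correct the one planned SAE comparison, where none of the safeguards above changes which events enter the statistic.

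**Conclusion.** The point holds as a comparability problem in SAE-based results, not as a failure to capture harm. As written, 21.2 lets an in-stay EBV complication go uncounted as serious when the same event causing admission in a control, or in the control year of a crossover, is counted. Prolongation is left undefined. The results exposed are the SAP X(b) McNemar comparison, any SAE rate shown by arm, and rehospitalisation when read as hospital-level burden.

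The likely direction favours the device, because the days just after placement are when the protocol watches most closely for pneumothorax. Delayed discharge works against that, so the net direction is a judgement. The size cannot be derived: about 25 expected pneumothoraces set the scale, but f and its counterparts for other complications are unknown, and any single percentage would rest on assumed fractions. The conclusion also assumes that no rule for the index stay sits in the consent or appendix pages that were not available. A clarification and a supplementary table are warranted; the main safety analysis does not need redesign.

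**What to change.** 1. Keep the 21.2 SAE counts. State that prolongation means a stay beyond the protocol's Day 5 discharge because of the event.
2. In SAP VII and X(b), add a supplementary category of hospital-level events: any event that meets 21.2, or that needed an invasive intervention (for example chest tube, intubation, or bronchoscopic re-intervention for a complication), whether or not the participant was already in hospital. Apply it identically to both arms and to both crossover years.
3. Tabulate it by arm beside SAEs and rehospitalisations, and repeat the McNemar comparison with it.

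An intervention rule is preferable to asking whether the participant would have been admitted from home. That question is a counterfactual judgement and would in effect be put to one arm only. The category is not perfectly neutral: Appendix 18 asks clinicians to consider a small-bore catheter for a pneumothorax of any size in higher-risk EBV recipients, so intervention counts partly reflect management. That is why it should stand beside the SAE counts and not replace them.

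The change affects reporting only, not care. The cost is some re-review of recorded in-stay events, for which onset, duration and action taken are already collected, and probably a somewhat less favourable EBV figure.

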21.3 Unanticipated Adverse Device Effects (UADE) and Reporting

Unanticipated adverse device effects (UADE) are defined as: Any serious adverse effect on health or safety or any life-threatening problem or death caused by, or associated with the study device, if that effect, problem, or death was not previously identified in nature, severity, or degree of incidence in the investigational plan, Investigator's Brochure, or package insert, or any other unanticipated serious problem associated with a device that relates to the rights, safety, or welfare of subjects. All unanticipated adverse device effects must be reported immediately (within 24 hours of knowledge of the event) to the study Sponsor. The Investigator must submit to the sponsor and to the reviewing IRB a written report as soon as possible, but in no event later than 5 working days after the Investigator first learns of the event.

A sponsor who conducts an evaluation of a UADE under CFR 812.46(b) shall report the results of such evaluation to FDA and to all reviewing IRBs and participating investigators within 10 working days after the sponsor first receives notice of the effect. Thereafter the sponsor shall submit such additional reports concerning the effect as FDA requests.

A sponsor who determines that a UADE presents an unreasonable risk to subjects shall terminate all investigations or parts of investigations presenting that risk as soon as possible. Termination shall occur not later than 5 working days after the sponsor makes this determination and not later than 15 working days after the sponsor first received notice of the effect.

21.4 Informed Consent Violation Reporting

If the Investigator uses an investigational device prior to obtaining informed consent from an intended study participant, the Investigator shall report such use to the sponsor and the reviewing IRB within 5 working days after the event occurs.

21.5 Protocol Deviation Reporting

The Investigator must notify the sponsor and the reviewing IRB of any deviation from the Investigational plan to protect the life or physical well-being of a study participant in an emergency. Such notice shall be given as soon as possible, but in no event later than 5 working days after the emergency occurred. All other deviations from the protocol will be reported on the appropriate case report form and reported to the IRB, if required.

21.6 Investigator Reporting

The Investigator must, upon request by the reviewing IRB/EC, FDA, or study sponsor, provide accurate, complete, and current information, or a summary report, about any aspect of the investigation.

22.0 STUDY DATA REPORTING AND PROCESSING

22.1 Study Data Collection

The Case Report Form set is designed to accommodate the specific features of the trial design. Modification of the CRFs may be done to ensure all required data is appropriately recorded. Significant modifications will be reviewed and approved by the Operations Committee.

22.2 Site Data Monitoring and Quality Control

Study coordinators or investigators at each clinical site will perform primary data collection based on source-documented hospital chart reviews. Case Report Forms will be submitted to data management in an expedited fashion.

To ensure proper tracking of Case Report Forms and test reports obtained from the individual clinical sites, a master tracking system will be utilized. Deficiencies identified by the master tracking system and any other specific clinical sites needs will be communicated regularly. In addition, regularly scheduled teleconferences between the Study Coordinator(s) for each site and the sponsor may occur.

All clinical sites will be monitored periodically by the sponsor's personnel, or sponsor's designee, for protocol adherence, accuracy of CRF completion, and compliance to applicable regulations. Ongoing and/or serious non-compliance with respect to these standards will be evaluated and appropriate corrective/preventive actions required will be determined. If corrective/preventive actions are not subsequently undertaken, the clinical sites will be asked withdraw from the study.

22.3 Communication

During execution of the study protocol, the sponsor will coordinate and host teleconference calls between the sponsor monitor, data management, and / or each clinical site, as necessary, to resolve any problems concerning the protocol and / or data collection. Every effort will be made to ensure compliance with the protocol. In addition, sponsor representative(s) will maintain personal contact with the Investigator and staff throughout the study by phone, mail, email and on-site visits. If problems cannot be resolved immediately, an appropriate expert(s) will be consulted.

22.4 Recruitment Tracking

A weekly recruitment status report generated by the master tracking system will be used regularly to identify variations in recruitment frequency among sites. For any well-balanced trial, a normal distribution in recruitment is expected; however, outliers will be investigated for trial compliance.

22.5 Data Processing and Quality Control

Data gathered during the course of the study will be reported on the study CRFs via a secure web-based database. The sponsor will evaluate all CRFs upon receipt. Missing, incomplete, or inconsistent data will be requested from the Investigator and corrections will be made. All efforts will be made to avoid loss of data. All changes will be appropriately documented. Passwords will be issued to appropriate personnel to ensure

confidentiality and protection of the data by allowing variable levels of access to the computer system.

